***Methemoglobin to be collected at 6 hours only**

DAY 1-3 (0-72 h post-ROSC) DATA

During post-ROSC days 1-3, the following data elements will be collected by a physician coinvestigator/research assistant prospectively or by a research assistant retrospectively. Refer to chart for visual of when labs will be drawn.

- Plasma labs measured variably between 24 and 72 h (troponin, arterial blood gas, lactate, plasma nitrite level, neuron specific enolase, ascorbate, cardiolipin, plasma banking)
- Urine labs measured variably between 24 and 72 h (renal failure and nitrated fatty acid measurements)
- *Full Outline of UnResponsiveness (FOUR) Score (components below)
- Eyes
- Motor
- Brainstem
- Reflex
- *Glasgow Coma Score (GCS)
- Eyes
- Verbal
- Motor
- EEG interpretation
- Dominant background present
- Reactivity present
- Seizures present
- Seizure type
- Burst-suppression ratio
- Estimate of survival to hospital DC
- Median nerve SSEP
- Witnessed aspiration
- New suspected infection last 24h
- Infection type
- Sputum color
- Vent mode
- Set Vt
- Set PC
- PEEP
- FiO2 (Use % oxygen)
- Peak Pressure
- Plateau Pressure
- CXR last 24h read may be pneumonia
- Positive airway culture last 24h

- Vital Signs (VS) (highest and lowest for each)
- Time to follow commands (assigned once)
- SOFA (worst in prior 24h period; some components may be missing)
- Respiratory (when no PaO₂ is available for PaO₂:FiO₂ ratio, use SpO₂:FiO₂ ratio)
- Nervous (based on GCS below)
- Cardiovascular
- Liver
- Coagulation
- Renal
- Interventions
- Coronary angiography
- PCI
- ECMO
- CPR
- CABG
- Mechanical ventilation hours
- NIPPV hours
- 24h FiO₂ AUC
- Tracheostomy
- Medications (dichotomous for use not dose)
- Alteplase
- Anti-epileptic
- Midazolam infusion
- Intermittent Benzodiazapine
- Propofol infusion
- Intermittent Propofol
- Opiate infusion
- Intermittent opiate
- Neuromuscular blockade infusion
- Intermittent neuromuscular blockade
- Neurostimulants
- *Vasopressors
- *Inotropes
- Ketamine
- Steroids (hydrocortisone/methylprednisolone)
- Cumulative vasopressor index (CVI; worst in prior 24h period)
- *BUN (highest value in prior 24 h)
- *Creatinine (highest value in prior 24 h)
- Hb
- WBC
- platelets
- PT
- INR
- PTT
- Bilirubin
- AST

- ALT
- BNP
- SvO2 (%)
- venous PaO2
- venous PaCO2

Research labs will be obtained by a study coordinator within 30 minutes of the assigned draw time. Labs will be run either within the UPMC Clinical Labs or the research labs of Drs. [name] or [name] as specified. We will also be collecting a small blood sample for an ancillary biomarker study for those subjects wishing to participate.

The final data to be collected will be the 90 d or discharge outcomes (whichever is later). Information that cannot be obtained by record review will be obtained either in person, or via a phone call by a member of the study team.

TABLE 1

Vital signs	Time from study drug start (hours)							
	0	3	6	9	12	24	48	72
Temperature	X	X	X	X	X	X	X	X
Heart Rate	X	X	X	X	X	X	X	X
Systolic Blood Pressure	X	X	X	X	X	X	X	X
Diastolic Blood Pressure	X	X	X	X	X	X	X	X
Mean Arterial Pressure	X	X	X	X	X	X	X	X
Arterial SBP	X	X	X	X	X	X	X	X
Arterial DBP	X	X	X	X	X	X	X	X
Arterial MAP	X	X	X	X	X	X	X	X
Pulmonary artery systolic pressure	X	X	X	X	X	X	X	X
Pulmonary artery diastolic pressure	X	X	X	X	X	X	X	X
Pulmonary artery mean pressure	X	X	X	X	X	X	X	X
Central venous pressure	X	X	X	X	X	X	X	X
Cardiac output	X	X	X	X	X	X	X	X
Vasopressors	X	X	X	X	X	X	X	X
Inotropes	X	X	X	X	X	X	X	X
Sedation	X	X	X	X	X	X	X	X
Neuromuscular blockade	X	X	X	X	X	X	X	X
Time from study drug start (hours)								
Labs (highlight represents UPMC Labs)	0	3	6	9	12	24	48	72
Troponin	X		X		X			
Arterial blood gas (ABG)	X		X		X			
Lactate	X		X		X			
Methemoglobin			X					
Neuron specific enolase (NSE)	X					X		
Plasma NO metabolites	X	X	X	X	X	X	X	X
Platelet mitochondria	X				X			
Ascorbate	X	X			X	X		
Cardiolipin	X	X			X	X		
Inflammation (integrin $\alpha 9\beta 1$ and CD11b)	X					X	X	X
Banked plasma	X	X	X	X	X	X	X	X
DNA for pharmacogenomics	X							
Whole blood pellet	X	X	X	X	X	X	X	X
Urine for renal failure markers and NO ₂ -cLA	X				X	X		
*DNA will be collected with the first scheduled blood draw after obtaining informed consent								

Outcomes

The following will be recorded at DC (+/- 3 days), and for follow up at day 30 (+/- 3 days) and day 90 (+/- 3 days) after OHCA:

*Survival

Cause of death

date/time of death

*CPC
*mRS
CPC-E
Barthel ADL
*NYHA Class
*Location of residence

2.3 STUDY DRUG

2.3.1. Study Drug Preparation and Dispensing

iNO used in this study will be sourced and formulated by INO Therapeutics, part of Mallinckrodt Hospital Products IP Limited. Cross reference authorization has been granted to us by Mallinckrodt for information on the study drug, known as INOmax under New Drug Application (NDA) 20-845. Placebo gas wherein nitrogen (the carrier vehicle gas) is substituted for iNO will also come from Mallinckrodt.

Mallinckrodt will deliver gas cylinders to the Respiratory Therapy (RT) Department at UPMC PUH or MER. Each cylinder will have a bar code which corresponds to its contents (iNO or placebo). Randomization will be done in advance in blocks of 8 at each site by the RT directors using the website <http://www.graphpad.com/quickcalcs/randomize1.cfm>. The random order list generated will list the order in which subjects coming in to each site are assigned to cylinders of study drug. In each group of 8, 4 subjects will be assigned to one placebo cylinder and 4 subjects will be assigned to one iNO cylinder. RT will dispense study drug upon patient enrollment and the blinded research assistant (RA) will transport the cylinder/iNOvent, making note of its barcode to permit subsequent treatment assignment, to the patient's bedside for connection to the ventilator by RT. All patients will be on mechanical ventilation via an endotracheal tube (ETT). iNO is a commonly used drug within UPMC and existing protocols for its use will be followed in connecting the drug to the ventilator circuit.

2.3.2. Drug Administration

Research subjects will be comatose, so no specific instructions will be provided to them. RT will connect the study drug to the mechanical ventilator and the drug will be dosed via ETT for the entire 12 h period at 20 ppm followed by a 1 h wean. All patients will receive the same pattern of administration.

2.3.3. Dose Selection

A number of studies have reviewed the safety of iNO in adults primarily in the setting of acute respiratory distress syndrome (ARDS). A recent meta-analysis found improved oxygenation but also greater acute kidney injury (AKI) resulting from iNO use.²⁵ When this was examined by dose, AKI only resulted in those patients receiving higher cumulative doses of iNO (≥ 40 ppm for ≥ 48 h).²⁶ Our study will limit iNO to 20 ppm for 12h hence AKI is not expected though we will track BUN and creatinine on all subjects. A separate meta-analysis examining effects of iNO in

acute hypoxic respiratory failure in adults and children found no associated adverse events.²⁷ A study of iNO used in transport identified no adverse events associated with the drug.²⁸ Although iNO significantly increases methemoglobin (metHb) levels, the increase (0.3%) is clinically insignificant and not associated with toxicity²⁹ which is uncommon until levels of 20-30% (we will consider > 10% a significant and unexpected adverse event). The best predictor of significant metHb >4% (as < 0-3% is considered within normal range) is cumulative iNO dose of >2000 ppm * h.³⁰ In our study subjects will receive only 250 ppm * h. We will monitor methemoglobin as part of our study at 6h. Although iNO lowers pulmonary blood pressure it has not been linked to reduction in systemic arterial blood pressure. We will monitor blood pressure effects closely in our study given the inherent instability of cardiac arrest subjects.

Effects of iNO after cardiac arrest has been studied in 4 preclinical animal studies.⁸⁻¹¹ These published studies demonstrated benefit using iNO 40 ppm started within 2h of ROSC which is additive to therapeutic hypothermia⁸ as well as neuroprotection without temperature control.⁹ These animal models include mouse and pig models of asystole and ventricular fibrillation (VF). In addition iNO has been shown to protect in animal models of focal heart¹²⁻¹⁵ and brain¹⁶⁻¹⁹ injury. This is important since most of the mortality and morbidity after OHCA results from heart and brain injury.²⁰

Animal models of asphyxia²¹ and other focal brain ischemia reperfusion models demonstrate NO deficiency early in reperfusion lasting at least 6h and benefits from iNO.^{16,19}

Information from prior clinical trials of iNO are available by cross reference in the Mallinckrodt NDA 20-845 (letter authorizing cross reference is included with application).

iNO is FDA approved for the treatment of pulmonary hypertension in the setting of hypoxic respiratory failure in neonates. It has been used off label extensively; primarily for the treatment of hypoxic respiratory failure and pulmonary hypertension. From these published studies, extensive safety data is available for a variety of endpoints with up to 2 year follow up.¹⁻⁶ In these studies efficacy as measured by increase in oxygenation was noted with doses as little as 1 ppm^{3,4} with rare cases of methemoglobinemia or excess NO₂ especially at the doses under 40 ppm. A recent meta-analysis of trials of iNO to treat ischemia reperfusion injury in humans demonstrated efficacy in the majority of studies and an excellent human safety profile, but noted no existing human evaluation of iNO in the setting of acute brain injury including OHCA.⁷

In human brain injury from stroke^{22,23} or trauma²⁴ the CSF levels of NO metabolites appear elevated by 24h with one study showing this effect is blocked using the inducible NO synthase inhibitor 1400W.²² Based on these reports it would appear a state of NO deficiency is highly likely at ROSC and persistent for up to 24h after ROSC. Thus the likely therapeutic window is from ROSC until 24h after ROSC.

Most studies that have demonstrated efficacy of iNO in animal models of CA or other IR injury have dosed the drug early (during CPR or at the time of ROSC). Only one study did a formal time course.³¹ In this report iNO started 2h after CA improved neurologic function/injury and survival but 6h later did not. Thus the therapeutic window is between CPR onset and <6h after ROSC. One study showed efficacy at 1h after ROSC.⁹ We selected a midpoint of 4h from ROSC as our latest time to initiate therapy but again stress that most data support earlier dosing either at the time of ROSC or during CPR. Thus our goal in designing a trial with recruitment under EFIC

is to enroll and dose patients as soon as possible after ROSC.

Our patients will generally achieve ROSC in the field (pre-hospital). Most patients at PUH, our larger center, arrive as transports already 1-3h post-ROSC upon arrival. Thus at the time the subjects arrive in our center we will be under substantial time pressure to get them on study drug even to achieve the goal of dosing prior 4h of ROSC. Furthermore, **many of these patients are flown into our center or transported by ambulance with sirens activated, thus arriving without a family member from whom to obtain consent.**

2.3.4. Treatment Period

RT will administer iNO at 20 ppm for 12h, with a 1h wean consisting of 10 min at 10 ppm, 10 min at 5 ppm, 10 min at 4 ppm, 10 min at 3 ppm, 10 min at 2 ppm, and 10 min at 1 ppm before subject is taken off of study drug.

2.3.5. Breaking the Blind

The safety monitor can request unblinding in the case of any serious unanticipated adverse event (SUAE) based on clinical judgement and will unblind whenever there is a MetHb level > 10% associated with any adverse event. The safety monitor will review clinical data from the study consisting of VS, vasopressor and inotrope use, labs and outcomes, at least every 4 weeks. In the event of a SUAE, the safety monitor will review the record within 48 h breaking the blind to determine whether this is a drug associated SUAE.

The Data Safety Monitoring Board (DSMB) will meet prior to the commencement of the trial and every 6 months. All data will be reviewed at 12 months or 60 subjects for safety. The DSMB and safety monitor are authorized to unblind at any time during the conduct of the study if they have safety concerns. The investigators will remain blind up until the point that the DSMB decides to halt the trial or trial conclusion.

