6.4.2 Data Safety Monitoring Plan

Data Monitoring Plan. The proposed study will use the FDA definition of adverse events (AE) and serious adverse events (SAE). Any SAE, which is unexpected and related to study intervention, will be reported immediately to the IRB and will be followed by an additional letter detailing the nature of the SAE. In the event that a participant either withdraws from the study or the investigators decide to discontinue a participant due to a SAE, the participant will be monitored by the co-PIs until (a) a resolution is reached (e.g., the problem has resolved or stabilized with no further change expected), (b) the SAE is determined to be clearly unrelated to the study intervention, or (c) the SAE results in death. Outcomes of SAEs will be regularly reported to the IRB and the sponsor. A summary of the SAEs that occurred during the previous year will be included in the annual progress report as well as in the annual IRB renewal.

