6.4.4 Frequency of Monitoring

The Investigator will review subject safety data as it is generated. The Investigator, sub-investigators, and the research staff will meet on a **monthly** interval to re-evaluate study goals, subject recruitment, data coding and retention, documentation and identification of adverse events, complaints and confidentiality of subjects. There will be an evaluation of the progress of the research study, including assessments of data quality, time lines, participant recruitment, accrual, and retention. The Investigator will also review the outcome and adverse event data to determine whether there is any change to the anticipated benefit-to-risk ratio of study participation and whether the study should continue as originally designed or

should it be re-evaluated and changed.

Independently the safety monitor will be review clinical data from the study consisting of subject VS, vasopressor and inotrope use and labs at baseline and during the first 24 h of enrollment (which includes study drug dosing) and final outcomes. This review will occur at least every 4 weeks. In the event of a SUAE, the safety monitor will review the record within 48 h, breaking the blind to determine whether this is a drug associated SUAE

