6.4.5 Reportable Adverse Events

This is a high risk population in which numerous serious adverse events are expected. Indeed, all subjects will require mechanical ventilation, with >50% of subjects expected to require >50% FiO₂ and/or vasopressors during the first 24 h based on our prior data^{33,34} and expected mortality is 70-80%³⁵ as we are excluding non-comatose subjects. Thus numerous serious adverse events (SAE) are anticipated during the conduct of this study with a complete list provided below. In this context we define a SUAE as any SAE that occurs in the setting of MetHb > 10% which may thus be attributed to the study drug.

Expected SAE (with severity grade indicated)

- Non-central nervous system thrombosis, particularly in vessels accessed for endovascular devices, assessed as symptomatic venous or arterial thrombus documented radiographically or ultrasonographically. (Grade 3)
- Sepsis assessed as the presence of microbiologically proven, clinically proven, or suspected infection; presence of Systemic Inflammatory Response Syndrome (SIRS); and development of at least one organ dysfunction within the preceding 24 hours. Diagnosis of SIRS will require the fulfillment of at least two of the following criteria (Grade 4):
 - Hyperthermia ($\geq 38^{\circ}\text{C}$) (which will only be evident after active temperature control);
 - Tachycardia ($\geq 90 \text{ bpm}$);
 - Tachypnea ($\geq 20 \text{ breaths/min}$) or an arterial pCO₂ $\leq 4.3 \text{ kPa}$ (32 mmHg) or mechanical ventilation;
 - White blood cell count $\geq 12,000/\mu\text{L}$ or $\leq 4,000/\mu\text{L}$ or left shift in differential white blood cell count $\geq 10\%$.
- Expected organ dysfunctions after OHCA (which may accompany SIRS in sepsis as defined above or separately) will be defined as:
 - Acute encephalopathy not explained by psychotropic medication (or attributable to the cardiac arrest) [Grade 3];
 - Thrombocytopenia $\leq 100,000/\mu\text{L}$ or drop in platelet count $> 30\%$ within 24 hours not explained by hemorrhage (Grade 3);
 - Arterial hypoxemia with an arterial pO₂ $< 8 \text{ kPa}$ (60 mmHg) when breathing room air or an oxygenation index (paO₂/FiO₂ $\leq 200 \text{ mmHg}$) not explained by presence of a pulmonary or cardiac disease (Grade 4);

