6.4.6 Adverse Events Reporting Timeline

All SUAE associated with the use of the study drug (ie in the setting of MetHb $> 10\%$ or discovered to be drug associated after unblinding by the safety monitor and considered potentially resulting from the study drug by the DSMB) will be reported to the IRB within 24 hours of discovery of the incident with subsequent follow-up submission of a detailed written report.

The FDA will be notified by telephone or facsimile transmission of a human SUAE no later than 7 calendar days after receiving the respective human adverse event information, followed by the

subsequent submission of a written IND Safety Report.

Serious and unexpected adverse events associated with the use of the study drug or procedures will be reported to the IRB with subsequent follow-up submission of a detailed written report in accordance with the respective policies and procedures of the IRB. Written IND Safety Reports will be submitted to the FDA as soon as possible and, in no event, later than 15 calendar days following the investigator-sponsor's receipt of the respective adverse event information.

A summary report of the findings will be prepared and submitted to the regulatory agencies.

6.4.7 Withdrawal of Subjects and Stopping Criteria:

Subjects withdrawn from the study due to concern for SAE will be followed for all clinical outcomes but no further lab or imaging data will be collected. These subjects will not be replaced within the study. Subjects will not be withdrawn after enrollment except if requested by the subject or surrogate after notification. In this event all data and specimens required for study outcomes obtained up to that time and clinical outcomes to DC will be retained.

Discontinuation of the Clinical Trial:

This study can be stopped only by the DSMB. In such a case we will complete collection of clinical outcomes in all enrolled subjects (up to 90 d after OHCA). Subjects will not be notified of early study termination.

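### For a serious unanticipated event without MetHb above 10%, the 24 h IRB notice depends on a 48 h unblinded review and an untimed DSMB view, so the notice can be late

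*Combined protocol and SAP*

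**What the plan says.** Four sets of provisions in the combined protocol and SAP bear on this.

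- **Monitor's review.** Section 2.3.5 says that, once a SUAE occurs, "the safety monitor will review the record within 48 h breaking the blind to determine whether this is a drug associated SUAE". Section 6.4.4 repeats the 48 h allowance.
- **24 h IRB notice.** Section 6.4.6 says that drug-associated SUAEs "will be reported to the IRB within 24 hours of discovery of the incident". It gives two ways to qualify, joined by an *or*. One is MetHb above 10%. The other is that the event was "discovered to be drug associated after unblinding by the safety monitor and considered potentially resulting from the study drug by the DSMB".
- **Other reporting statements.** Under section 6.4.2 any SAE that is unexpected and related to the intervention "will be reported immediately to the IRB". The same section has staff report every adverse event at once to an investigator, who passes it to the IRB under standard procedures. Section 6.4.6 also sends serious and unexpected drug-associated events to the IRB under IRB policy. It gives the FDA a written report within 15 calendar days, and notice of a SUAE within 7.
- **Definition of SUAE.** In section 6.4.5, "we define a SUAE as any SAE that occurs in the setting of MetHb > 10" per cent, and section 2.5.4 repeats this. Section 2.3.5 uses the term more widely: "The safety monitor can request unblinding in the case of any serious unanticipated adverse event (SUAE) based on clinical judgement". It then treats MetHb above 10% as a separate trigger for unblinding.

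Under section 6.4.2 the DSMB meets every 6 months, and its chairperson may call an emergency meeting at any time. No turnaround is stated for a view on a single event.

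**The concern.** A 24 h deadline is tied to a decision that is allowed 48 h, and then to a second body's opinion that has no time limit. A team that uses the time the protocol allows can therefore miss the protocol's own deadline.

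The affected route matters because the other one should rarely apply. Section 2.3.3 links MetHb above 4% to a cumulative dose above 2000 ppm·h and puts this trial at 250 ppm·h. It calls a level above 10% unexpected. MetHb is scheduled once, at 6 h (Table 1). A drug-related event that is serious and unanticipated would therefore more probably have to qualify through the monitor and the DSMB.

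Under section 2.3.5 the investigators stay blind until the DSMB halts the trial or the trial ends, so they cannot supply the unblinded finding themselves. Subjects are enrolled under exception from informed consent, which makes prompt IRB notice one of the main outside safeguards.

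**Working it through.** This is a comparison of time limits, and the plan has no figure of its own to reproduce.

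**Inputs**
- Monitor's determination: m hours after the start of review, with m at most 48 (2.3.5, 6.4.4). The start is not defined beyond the occurrence of a SUAE. I assume that it is the discovery of the event.
- IRB notice: 24 h from discovery of the incident (6.4.6).
- DSMB view: D hours, not stated.

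**MetHb above 10%.** The event qualifies without the monitor or the DSMB, so there is no conflict.

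**No MetHb above 10%, broad use of SUAE (2.3.5, 6.4.6).** The event qualifies at hour m + D.

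| Start of the 24 h clock | Report due | Event qualifies | Result |
|---|---|---|---|
| Discovery of the event | hour 24 | hour m + D | late by m + D − 24 when this is positive |
| Attribution by monitor and DSMB | hour m + D + 24 | hour m + D | never formally late, but D has no limit |

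- First row with D = 0: the delay runs from none (m at most 24) to 48 − 24 = 24 h (m = 48). Any DSMB time adds to it.
- Second row with m = 48: the report may come 48 + D + 24 = 72 + D hours after the event.
- If the clock starts at the monitor's finding alone, the 48 h falls before it. The untimed DSMB view must then fit inside the 24 h.

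**No MetHb above 10%, narrow definition of SUAE (2.5.4, 6.4.5).** Every SUAE then has MetHb above 10% and qualifies directly, so the clash of 48 h with 24 h disappears. The second way of qualifying in 6.4.6 is then empty. A serious unexpected event without raised MetHb has no 24 h rule and falls to 6.4.2 or to IRB policy.

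Each reading leaves a gap or a conflict, and the text does not say which is meant.

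**The case against.** The strongest reply is that 48 h is a maximum. A monitor and a DSMB that both finish by hour 24 satisfy every sentence. This stands: the rules can all be followed, and the overrun is possible, not certain.

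A second reply is that 6.4.6 speaks of an event being discovered to be drug associated, so discovery could mean attribution. That is arguable, but the deadline is attached to the incident, and the DSMB step would still be untimed.

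A third is that the narrow SUAE definition removes the clash. It does, but only by leaving half of the 6.4.6 sentence without content.

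There are also stronger readings that the documents do not support.

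- **That the event could go unreported.** Section 6.4.2 has immediate reporting of unexpected related SAEs and routine reporting through the investigator. Section 6.4.6 has the IRB-policy and 15-day FDA reports. None of these is stated to depend on the monitor or the DSMB.
- **That the delay could run to about six months.** This ignores the emergency meeting, and the role of the DSMB chairperson as contact for serious adverse event reporting.
- **That heart failure, hypoxia or kidney injury, named as risks in 6.1.1, would be held up.** Section 6.4.5 lists pulmonary edema, arterial hypoxemia and renal dysfunction as expected SAEs. They would not ordinarily enter this route.

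**Conclusion.** The conflict is real but narrow. It concerns only the 24 h IRB notice for a serious unanticipated event without MetHb above 10%. On the plain reading of the clock, and with the monitor's review also starting at discovery, that notice can be up to 24 h late before DSMB time is counted. If the clock starts at attribution, the lateness becomes an open-ended wait for the DSMB. What is at risk is the timing of one expedited notice. The two meanings of SUAE compound the problem, because they decide whether the route exists at all.

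The sponsor should correct this, since it concerns safety reporting in a trial that enrols without prior consent. It has no bearing on sample size, power, type I error or the analysis of the primary endpoint.

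**What to change.** Reconcile sections 2.3.5, 2.5.4, 6.4.2, 6.4.4, 6.4.5 and 6.4.6:

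1. Define SUAE once and use that meaning throughout, so that it is clear whether events without MetHb above 10% are covered.
2. State when the 24 h IRB clock starts, and start the monitor's review from the same moment.
3. Make the monitor's review window fit inside the IRB limit.
4. Do not make the IRB report wait for the DSMB. Inform the DSMB in parallel and send its view as follow-up.
5. Make the immediate-reporting sentence in 6.4.2 refer to the same rule.

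Other wordings could also reconcile the text, provided that they settle the definition, the clock start and the DSMB condition. The cost is a protocol wording change, a faster turnaround for the safety monitor on rare events, and some reports later judged unrelated to the drug.

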2. RESEARCH DESIGN AND METHODS

2.1 CLASSIFICATION AND METHODOLOGICAL DESIGNS

The iNO OHCA study is a phase II double blind (participants and investigator) placebo controlled randomized (1:1) clinical trial of iNO 20 ppm administered over 12h (with 1 h weaning off) beginning as soon as possible but within 4 h of return of spontaneous circulation (ROSC) after OHCA. Planned enrollment is 130 subjects over 24 months at UPMC Presbyterian (PUH) and Mercy (MER) with randomization stratified in blocks of 8. Recruitment will be performed under exception from informed consent (EFIC) to facilitate early enrollment and treatment. The study will have a safety monitor to assess any concerns during its conduct and a pre-specified safety analysis at the mid-point (after 1 year or 60 patients whichever occurs first). Subjects or their surrogate (as subjects will be enrolled when comatose) will be notified as soon as possible by a member of the research team of enrollment and can elect whether to permit blood banking for future genetic studies.

Duration of subject participation is 90 ± 3 d of ROSC. Most data will be collected within four days of ROSC, which includes the 12h of study drug administration and 1h weaning of study drug. After the initial four days have passed follow up will be done at hospital discharge (DC; which includes death), day 30, and day 90 after OHCA to evaluate outcomes.

Subjects will not be withdrawn from or prevented from receiving any known effective therapy for the purposes of participating in this research.

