2.4 STUDY ENDPOINTS

Primary

Composite of in-hospital death, unfavorable discharge location, NYHA class III/IV heart failure at the time of discharge*

*In the setting of pre-existing heart failure or prior residence in an unfavorable location there must be at least a 1 class decrement (eg NYHA III -> IV)

Secondary

Functional

- Survival to hospital discharge, 30 and 90 days after initial OHCA
- Favorable cerebral performance category (CPC) defined as 1 or 2 at discharge, 30 and 90 days after initial OHCA
- Favorable modified Rankin score (mRS) defined as 0-3 at discharge, 30 and 90 days after initial OHCA
- Favorable discharge destination or location of residence (30 and 90 days after OHCA) defined as home or acute inpatient rehabilitation
- CPC-E at hospital discharge, 30 and 90 days after initial OHCA
- Barthel Index of Independence in Activities of Daily Living (ADL) at discharge, 30 and 90 days after OHCA

Neurologic

- Estimated likelihood of good neurologic outcome (0-100%) assessed by an experienced (>3y) member of the PCAS team blinded to treatment assignment on day 3-5 post-ROSC.
- Development of malignant EEG during hospitalization

- Time (in hours) to awakening from ROSC; defined as following commands (all values > 96h assigned 100)
- FOUR Motor + Brainstem scores on days 1-3 (requires 30 min off sedation; exclude endpoint if not medically permitted to pause sedation or paralysis)
- Presence or absence of upper and lower extremity somatosensory evoked potential N20 on comatose patients obtained any time after post-arrest day 1.
- Absolute value 24h after ROSC and change in value (24h vs 0h) of neuron specific enolase (NSE)
- EEG burst suppression ratio and change in suppression ratio
- EEG presence of dominant continuous background and reactivity to photic or tactile stimulation.

Cardiovascular

- Heart rate and mean arterial pressure (preferably off the arterial line) at 0-12 (hourly), 24h of study drug
- Persistent need for vasopressors in the first 24h after ROSC; defined as any use of norepinephrine, epinephrine, phenylephrine, dopamine or vasopressin for ≥ 3 h after study drug is initiated
- Persistent need of inotropes in the first 24h after ROSC; defined as any use of epinephrine, dobutamine, milrinone or isoproterenol for ≥ 3 h after study drug is initiated.
- ECHO measures (absolute values at end of therapy (12h) and change in 12h vs 0h):
 - tricuspid valve regurgitant velocity (TRV)

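### After an early stop, the plan no longer protects the investigators' blind while judgement-based outcomes are still being collected to day 90

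*Combined protocol and SAP*

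**What the plan says.** Section 2.3.5 sets the end of the blind: "The investigators will remain blind up until the point that the DSMB decides to halt the trial or trial conclusion". It does not define trial conclusion.

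Section 6.4.7 adds two things. First, "This study can be stopped only by the DSMB", so every early stop takes this route. Second, follow-up goes on afterwards: "In such a case we will complete collection of clinical outcomes in all enrolled subjects (up to 90 d after OHCA". It also says that subjects will not be told of an early termination. It gives no matching rule for the people who assess outcomes.

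Section 2.1 fixes the time points: "follow up will be done at hospital discharge (DC; which includes death), day 30, and day 90 after OHCA to evaluate outcomes". Section 2.2 lists what is recorded at each: survival, CPC, mRS, CPC-E, Barthel ADL, NYHA class and location of residence. Anything that record review does not supply is "obtained either in person, or via a phone call by a member of the study team".

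On who is blind, section 2.1 describes a "phase II double blind (participants and investigator) placebo controlled randomized (1:1) clinical trial". Outcome assessors are not named as a separate blinded group. The one clinical endpoint with an explicitly blinded assessor is the early prognosis estimate in section 2.4, "assessed by an experienced (>3y) member of the PCAS team blinded to treatment assignment on day 3-5 post-ROSC". Section 2.2 makes the PCAS physicians, who are consulted in these patients' care, co-investigators.

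**The concern.** NYHA class, CPC, mRS, CPC-E and Barthel all need some judgement from the rater or the respondent. Section 6.4.2 lets the DSMB recommend termination because of observed benefit or harm, so a halt can itself tell the team which direction to expect. If a rater also learns a subject's arm, the ratings still to come can lean that way. This would happen in the scenario where the trial's data are read most closely.

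The cylinder scheme makes a disclosure spread. Under section 2.3.1 each group of eight uses one placebo cylinder for four subjects and one iNO cylinder for the other four. Section 2.2 stores the cylinder bar code with the subject ID in the study database. Learning what one cylinder contains therefore identifies four subjects directly and the other four in the block by elimination.

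The undefined term raises a second question. If trial conclusion were read as the end of enrolment, the same loss of protection would occur at a normal finish.

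**Working it through.** The plan gives no figure on this point, so there is none to reproduce. The check has two parts: the rules side by side, then the number of subjects affected.

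**The rules**
- Commitment to stay blind: ends at the DSMB's decision to halt (2.3.5).
- Outcome collection: continues to day 90 after that decision (6.4.7).
- Who collects: records first, then a study team member in person or by phone (2.2).
- Safeguard for raters between the halt and the last outcome: none in the sections read.

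The two rules can both be followed. Following both leaves up to 90 days in which ratings are made without any commitment that the raters are blind.

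**Inputs**
- Accrual: 130 subjects over 24 months (2.1).
- Participation: 90 ± 3 days from ROSC (2.1).
- Interim look: 1 year or 60 subjects, whichever is first (6.4.2).
- Expected mortality: 70-80% (6.4.5), so 20-30% survive.
- Hospital stay: not in the documents; 7, 14 and 21 days are assumed.

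**Subjects within follow-up at a halt** (even accrual assumed; count = monthly rate × window in days / 30.4375)
- Rate: 130/24 = 5.42 per month.
- 90 days: 5.42 × 90/30.4375 = 16.0.
- 93 days: 5.42 × 93/30.4375 = 16.6.

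**Survivors among them with functional ratings pending**
- Low: 0.20 × 16.0 = 3.2.
- High: 0.30 × 16.6 = 5.0.
- The 60th subject is reached at 60/5.42 = 11.1 months, before one year. As a share of 60: 3.2/60 = 5% and 5.0/60 = 8%.
- For scale, total expected survivors among 60 are 0.20 × 60 = 12 to 0.30 × 60 = 18.

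**Subjects with the primary composite still open** (still in hospital)
- 7-day stay: 5.42 × 7/30.4375 = 1.2.
- 14-day stay: 2.5.
- 21-day stay: 3.7.

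Any of these who die in hospital reach the composite through death, which needs no rating.

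**The case against.** The best case against the point is that section 2.3.5 says how long investigators must stay blind, not that anyone is told the assignments afterwards. That stands. A reader might infer that the team collects the remaining outcomes unblinded, but the documents do not say so. Section 2.2 leaves the allocation lists with three people who take no part in conduct or analysis, and the bar code in the database means nothing without those lists. What is lost at a halt is the plan's protection, not necessarily the blind itself.

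A reader might also take the 16 to 17 subjects, about 28% of 60 (16.6/60), as the size of the problem. That is too large. Most of them are expected to die, and death is not a matter of judgement. Many of the survivors would already have their discharge rating, and some their day-30 rating, recorded before the halt.

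The plan has partial safeguards: records are consulted before anyone is telephoned, and subjects are not told of the halt. Two of the three primary components, death and discharge location, are recorded facts. The date of a halt is known, so analyses restricted to outcomes recorded before it, or to survival, are possible. It would be wrong to say that analysis can do nothing, although the first of these discards the later ratings rather than repairing them.

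Two things cannot be checked. Section 8.1, which section 6.5.2 cites on qualifications for data acquisition, was not in the text read. Section 6.4.2 leaves the DSMB's monitoring guidelines to its first meeting. Either might assign raters or restrict disclosure.

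None of this supplies a rule that keeps raters blind after a halt.

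**Conclusion.** The point holds as a gap in protection. After a DSMB halt, the plan stops requiring investigators to be blind while judgement-based ratings are still due. It does not establish that raters would in fact know the assignments.

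The size is small and conditional on an early stop: about 3 to 5 survivors with functional ratings pending, 5-8% of 60 at the interim look, and about 1 to 4 subjects with the primary composite open. The first range rests on even accrual and the plan's own mortality figure. The second also rests on a stay of 7 to 21 days, which is an assumption. Recorded survival status is not affected. The change is worth making because it is cheap and the exposure is avoidable.

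**What to change.** Reword section 2.3.5 along these lines: investigators and everyone who assesses outcomes remain blinded until the last enrolled subject's final outcome (day 90, or discharge if later) has been entered and the database locked, including after a DSMB decision to halt. Earlier release is allowed only for an individual subject's safety or where IRB or FDA safety reporting requires it, and is confined to those who need it. The reporting exception is needed because section 6.4.6 sets deadlines from 24 hours to 15 calendar days, and confinement matters because one cylinder decodes a block of eight.

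Leave the DSMB's and the safety monitor's powers to unblind as they are, and cross-refer from section 6.4.7. The same wording settles what trial conclusion means for blinding at a normal finish.

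No new staff are needed, since the lists are already held outside the study team. The cost is that the team waits up to about three months after a halt to learn the assignments.
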